⁵ Stocking is defined as whether there has been a stockout in the 90 days prior to the facility visit by the survey team.

⁶ Pediatric amoxicillin refers to the two primary pediatric formulations of amoxicillin that are intended for use with children under five, Amox-DT and amoxicillin oral suspension/syrup (Amox-OS)

⁷ The in-person round includes an additional secondary aim: Assess how providers alter prescription behavior when faced with a peds-Amox stock out. As described in the footnote above, no interview is conducted with health care providers in the remote rounds.

I. Research Questions & Indicators

The goal is to monitor whether Amox-DT, and peds-Amox more broadly, are reaching health facilities and being dispensed to children appropriately. The four main research questions that guide Phase II are⁸:

1. What is the availability of peds-Amox in public health facilities?
2. Has the availability of peds-Amox in public health facilities changed over the past three years? If so, by how much?
3. What are the stocking levels of peds-Amox in public health facilities?
4. Has the stocking of peds-Amox in public health facilities changed over the past three years? If so, by how much?

The primary and secondary outcomes from the survey used to explore each of these questions are presented in the Outcomes section, in *Table 1*.

II. Sampling Method

Phase I

Prior to Phase I, R4D worked with the MoHCDGEC to obtain a list of all public health facilities in Tanzania at three levels: district hospitals, health centers and dispensaries. Using this list, we implemented a stratified two-stage sampling method to select a nationally representative sample of public health facilities across the 26 mainland regions of Tanzania to be included in the baseline and subsequent rounds of data collection. The sampling process is outlined below.

1. Randomly selected three districts from each of the 26 regions of mainland Tanzania^{9,10,11}
2. Randomly selected facilities based on the category of facility from each council:
 - One district hospital was selected per district (if available)¹²
 - One health center was selected per district (if available)
 - Seven dispensaries were selected per district¹³

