⁸ In line with the explanation above, the in-person round includes an additional research question related to interviews with health care providers: Has provider knowledge of proper pneumonia diagnosis and treatment changed over the past three years? In the remote rounds, no interview is conducted with health care providers.

⁹ One and two councils were sampled from Mbeya and Songwe regions, respectively. In 2016, the Songwe region was created from the western part of Mbeya region. Two councils in Kagera region were excluded because the survey was piloted in those areas. Two councils from Arusha region were replaced at the request of the survey firm, EDI, due to the councils being located inside national parks, which would have presented significant logistical difficulties.

¹⁰ Councils were weighted according to the proportion of public health facilities in each council so that councils with a higher number of public health facilities would have a greater probability of selection.

¹¹ The list of active public health facilities at the dispensary, health center, and district hospital level was downloaded from MoHCDGEC's Health Facility Registry in January 2017.

¹² District hospitals were over-sampled since one of the survey objectives focused on the availability of electricity and oxygen at district hospitals.

¹³ Districts with fewer than seven dispensaries included all dispensaries.

This resulted in a total sample of 624 health facilities. The sample was comprised of 53 district hospitals, 50 health centers, and 521 dispensaries, out of a total of 61 district hospitals, 477 health centers, and 4,471 dispensaries in Tanzania (according to Tanzanian Government Open Data information from July 2016). When possible, the same facilities were surveyed in each round of data collection to allow outcomes within each facility to be compared over time.

Phase II

For the eight rounds of data collection in Phase II, we selected a sub-set of approximately 250 health facilities from the 2017 Phase I sample of public health facilities using a geographically stratified randomization approach. The sampling process was as follows:

1. Ran power calculations and determined the need to select 10 regions.
2. Randomly selected one region from each of the eight geopolitical zone in Tanzania,¹⁴ for a total of eight regions selected.

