3. Purposively selected the Dar es Salaam and Mwanza regions to ensure population and urban representation, resulting a total of 10 regions selected.

In the 2017 study, there were an average of 25 facilities sampled per region, across three districts. All facilities from the 2017 Phase I sample in these ten regions were included in our Phase II sample, resulting in a sample size of 251 health facilities. This approach will allow outcomes to be compared over time within each facility from 2017 to 2021 and allows to detect a change of 8.51 percentage points.

If a facility is permanently closed over the course of Phase II data collection, a facility of the same category (district hospital, health center, dispensary) will be randomly selected from the same district to serve as a replacement facility in the sample.

III. Data Collection

Round 1 of Phase I was conducted in March 2017,¹⁵ Round 2 was conducted in July 2017, and Round 3 was conducted November 2017.

Data collection for the first remote round of Phase II will be conducted over 3 weeks from May 12, 2020 to June 8, 2020.

Data collection methods

The remote public health facility survey employs a CATI data collection method in which enumerators speak with respondents over the phone and record responses in a tablet as the responses are given. The

¹⁴ Geopolitical zones were defined as those used in the 2015/2016 Demographic and Health Survey (DHS) and 2017 Malaria Indicator Survey.

¹⁵ The first round of data collection in March 2017 was intended to serve as a baseline measure of Amox-DT availability, stocking, and dispensing before R4D-funded Amox-DT reached health facilities. However, since peds-Amox had already reached emergency stocking levels nation-wide, R4D and the MoHCDGEC agreed to start Amox-DT distribution upon its arrival in country in late 2016. The first shipment of R4D-administered Amox-DT reached MSD zonal stores on January 15, 2017 and began distribution to health facilities shortly thereafter.

survey is a structured interview that includes requests for respondents to conduct stock counts and carry out record reviews.

The survey is comprised of three questionnaires:

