- 1. Facility questionnaire:** Conducted with the facility in-charge to obtain consent to survey health facility staff and collect data remotely; identify potential respondents for the remote data collection rounds; and gather background information about the facility and information on the availability of oxygen treatment, pulse oximeters, and electricity.
- 2. Respondent introduction questionnaire:** Conducted with the staff member identified by the facility-in-charge as someone who is familiar with the availability and stocking of pediatric medications at the facility, typically the stock room in-charge or stock room attendant. The goal of this questionnaire is to introduce the respondent to the remote data collection methodology and provide an instructions sheet on how to collect the medicine availability and stock levels of peds-Amox and other comparator medicines from facility dispensing outlets and stock rooms.
- 3. Dispensing outlet and stock room questionnaire:** Conducted with the same staff member who participated in the respondent introduction questionnaire (questionnaire 2). The goal of this questionnaire is to assess availability of peds-Amox and other comparator medications, as well as to record the stocking levels of peds-Amox in all dispensing outlets (excluding Care and Treatment Clinics, or CTCs) and all stock rooms at the facility.

Table A1 in the *Appendix* summarizes the three questionnaires.

Survey Firm

For Phase II data collection, R4D is partnering with the same survey firm, EDI Global, that conducted the three initial rounds of data collection in Phase I.

EDI Global (EDI) is responsible for:

- Recruiting and hiring the enumerator team
- Programming the data collection tools in proprietary software, Surveybe@
- Translating tools and instructions into Swahili
- Conducting enumerator training
- Managing the logistics of data collection
- Administering surveys
- Supervising enumerators to ensure high quality data collection
- Collating and cleaning the data

The EDI data collection team is led by a Team Leader and Project Coordinator with the assistance of a Data Processing Officer. The survey is being conducted by four enumerators who are overseen by two supervisors.

Quality assurance measures

Several quality assurance measures are being implemented by EDI to ensure high-quality data, along with oversight measures by R4D. Quality assurance measures include:

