Our aim is to explore how outcomes have changed within facilities, on average, as a result of three years of R4D's catalytic funding. We will use the bivariate fixed effects regression reported in [Eq 3a]. Standard errors will be clustered at the facility level. This model measures the change in an outcome within each facility over time and takes the mean across all facilities in the sample. In this specification, each facility has outcomes measured at two points in time – in other words, all of the outcomes are “paired.”

This model will be used to analyze outcomes for facilities which had data in both Phase I, Round 1 and Phase II, Round T , where T is the round of interest. The analysis will be repeated on every outcome metric listed in *Table 1*.

$$Y_{jt} = \beta_0 + \beta_1 R_j + \sum_{j=1}^N \beta_{2,j} \eta_j + \varepsilon_{jt} \quad [\text{Eq } 3a]$$

Y_{jt} is the value of the outcome variable for facility j in round $t=T$, where T is the round of interest. Y_{jt} will be one of the outcome metrics listed in the right column of *Table 1*; the regression will be run for all outcome metrics in the table. R_j is an indicator variable equal to 1 if the observation for facility j is from Phase II, Round T of data collection or 0 if the observation is from Phase I, Round 1 (the “baseline”). The coefficient on R_j , β_1 is our coefficient of interest. β_1 will report the mean effect of three or more years of R4D's catalytic funding on our outcomes of interest. $\sum_{j=1}^N \eta_j$ represents facility category (hospital, health center, or dispensary) fixed effects. This is a set of dummy variables for each facility category; one category will be omitted to prevent collinearity. ε_{jt} is the error term for facility j in round t . Subscripts specify the observation: j identifies the individual facility, and t denotes the data collection round. We elected to use facility type rather than individual facility characteristics as with the limited data collection, many facility characteristics are highly correlated with facility type.

Second Specification: Unpaired Outcomes Analysis

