of tests, the next most significant results with a factor equal to the total number of tests – 1, etc.¹⁷ The benefit of the Holm-Bonferroni test is that it accounts for outcomes that are dependent in a less conservative way than Bonferroni, thereby improving the statistical power of the test.¹⁸ For this correction, our “families” of hypotheses are as outlined in *Table 1*.

II. Missing Data

Missing values can take the form of non-response (e.g. uncompleted surveys), partial response (e.g. “Don’t know” responses), or errors in the data. Minor and random missing values can be omitted from the analysis. If we find that missing values are unexpectedly high, we may check the sensitivity of the complete case estimate using imputation methods to replace missing values. However, we expect minimal missing data since the digital survey form includes constraints that require data to be entered before the enumerator can proceed with data collection.

There are three main reasons a facility surveyed at baseline may not be surveyed in Phase II data collection rounds:

1. Temporary closures – In Phase I, Round 2, two facilities from the original sample were not surveyed due to temporary closures. These two facilities were reopened for Phase I, Round 3 surveying, but we may see other facilities drop from the Phase II sample for similar reasons.
2. Permanent closure – If a public health facility surveyed in Phase I has since closed, we will randomly select another public health facility of the same level from the same district not previously included in the study.
3. Inability to contact facility – Before the in-person round of Phase II was suspended, the survey teams visited 97 facilities of the 251 Phase II facilities and collected new contact information. The 154 remaining facilities will need to be contacted using phone numbers provided by the District Medical Officer (DMO) and phone numbers collected in Phase I. If these numbers are incorrect or outdated, we may not be able to contact the health facility. In this instance, we will randomly select another public health facility of the same level from the same district not previously included in our survey.

III. Evaluation Effects

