There is some risk of various evaluation effects (also known as observer, or Hawthorne, effects), the process by which a participant of a study changes their behavior due to the knowledge that they are under study and for what specific purpose. For example, healthcare workers may try to request (unnecessarily)

¹⁷ In practice, this is performed by sorting outcomes into groups called families whereby outcomes or tests within a family are correlated (dependent). Following outcome sorting, the change in the outcome across survey rounds is estimated using either model. Unadjusted p-values from each test within a family are then sorted in ascending order and corrected by multiplying the p-value of a given rank by $(m - n)$, where m is the total number of tests within a given family of related outcomes and n is the rank order of the p-value from 0 (smallest) to m (largest). If the adjusted p-value is less than 0.05, then that outcome is statistically different between rounds.

¹⁸ Abdi, H (2007). Bonferroni and Šidák corrections for multiple comparisons. *Encyclopedia of measurement and statistics*, 3, 103-107.

additional Amox-DT stock if they have knowledge that this is one of our primary outcomes – and especially if they discern that we think having Amox-DT stock is desirable. For these reasons, the survey tool contains additional questions about other treatments for childhood illnesses to lessen the likelihood that a healthcare worker will identify pneumonia and its associated treatments as being our major outcome of interest. By doing so, we also aim to decrease the risk of the observer effect influencing the quality of our data.

IV. Other Study Limitations

Additional limitations of this study are due to data sources, time constraints, and potential respondent biases.

These limitations include:

- The quality of the data differs based on the data source. The research team may be able to collect observable and verifiable data in some cases but will have to rely on respondent recall for others. For example, the research team may be able to verify if the medications were available in the stock rooms and dispensing outlets on the day of the visit. However, data on stock outs relies on a combination of records and recall, dependent on whether the respondent has records available for reference as well as the quality of those records.

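### Every remote-round change from Phase I Round 1 is also a change from apparent facility visits to telephone self-counts, and nothing in the plan separates the two

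*Combined protocol and SAP*

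**What the plan says.** All references are to the combined protocol and SAP.

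- **Remote mode.** Data collection methods: "The remote public health facility survey employs a CATI data collection method", and the "survey is a structured interview that includes requests for respondents to conduct stock counts and carry out record reviews". The respondent introduction questionnaire exists to introduce the remote method to staff and to "provide an instructions sheet on how to collect the medicine availability and stock levels of peds-Amox" and other medicines.
- **Baseline mode.** Not stated. Footnote 5 reads "Stocking is defined as whether there has been a stockout in the 90 days prior to the facility visit by the survey team". Footnote 9 says two Phase I councils were replaced "due to the councils being located inside national parks, which would have presented significant logistical difficulties".
- **Model.** In Eq 3a and Eq 4a, R is 1 for "Phase II, Round T of data collection or 0 if the observation is from Phase I, Round 1". Its coefficient β1 is described as the mean effect of three or more years of the sponsor's funding.
- **Limitations.** Other Study Limitations lists data-source quality, respondent availability, refined tools and different respondents. It does not list survey mode. It still says the team "may be able to verify if the medications were available in the stock rooms and dispensing outlets on the day of the visit".
- **The suspended in-person round.** Missing Data says "the survey teams visited 97 facilities of the 251 Phase II facilities and collected new contact information". No other use of those visits is planned.

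**The concern.** The change-over-time analysis is meant to show how availability and stock-outs moved between Phase I Round 1 and each Phase II round. If shelves were seen by an enumerator at baseline and are counted and reported by staff over the phone in Phase II, a difference in how stock is reported cannot be told apart from a difference in stock. Both primary outcomes are exposed, and so are all seven remote rounds.

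The section on changes over time disclaims a definitive causal reading, but only for lack of a true baseline and of randomization. It then says that the controls, fixed effects, clustering and robustness checks allow the effect of the sponsor's activities to be estimated net of other changes. For survey mode they do not. The original design opened Phase II with an in-person round, which would have given an early same-mode comparison. When that round was suspended, the analysis was not adapted.

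**Working it through.** **1. Is mode separable from round?** In every remote comparison, phone = 1 exactly when R = 1. Write Δ for the true change and m for the mean shift in the reported outcome caused by mode. Then E(β1) = Δ + m. The terms on offer are facility category, individual facility, region and strata fixed effects, the purely-random indicator S, and the facility variables X. None is a mode term, and none could be, because mode does not vary within a round.

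**2. Was the baseline by visit?** Three pieces of text point that way: the visit wording of footnote 5, the councils replaced for logistical reasons, and the remote method being introduced to respondents in Phase II. The first is weak, because this remote-round plan also uses visit wording for its own rounds. The second is better but indirect. It is a strong inference, not a stated fact.

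**3. The plan's own figure.** The 8.51-point detectable change with 251 facilities comes without power, sidedness, baseline rate or correlation, so it cannot be uniquely reproduced. At 80% power, two-sided 5%:
- paired, (1.96 + 0.84) × √(d/251) = 0.0851 needs a discordant share d of 23.2%;
- unpaired, 251 per round, it needs a baseline rate of about 0.82.

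Both are plausible, so the figure is neither confirmed nor refuted. It is used below only as a scale: SE = 8.51/2.80 = 3.04 points.

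**4. What a mode shift would do.** With Δ = 0 and SE 3.04, an unadjusted two-sided 5% test rejects as follows.

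| Mode shift m (points) | Rejection |
|---|---|
| 1 | 6% |
| 2 | 10% |
| 3 | 17% |
| 5 | 38% |
| 8.51 | 80% |

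**5. Which direction?** For availability, m = (1 − p) × a − p × b. Here p is true availability, a the share of empty facilities reported as stocked, and b the share of stocked facilities reported as empty. With assumed p = 0.70:
- a = 0.20, b = 0: 0.30 × 0.20 = +6.0 points;
- a = 0, b = 0.10: −0.70 × 0.10 = −7.0 points;
- a = 0.10, b = 0.05: 0.030 − 0.035 = −0.5 points.

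The documents give no values for a or b, so neither sign nor size follows from them.

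**6. Could the visited facilities help?** Study Aims prints the start of the in-person round as March 9, 2019, but the COVID-19 context fits 2020. Reading it so:
- calls on May 12 and June 8, 2020, less 90 days, look back to February 12 and March 10;
- a facility seen without peds-Amox in March should therefore report a 90-day stock-out by phone, whatever was delivered later. The exception is an edge case: March 9 to June 8 is 91 days;
- the gap between visit and call is about 8 weeks (March 16 to May 12, 57 days) to 13 weeks (91 days).

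**7. How precise would that be?** If 20–40% of the 97 were out of stock when visited (assumed), 0.20 × 97 ≈ 19 to 0.40 × 97 ≈ 39 facilities are informative. The 95% Wilson interval for the missed share is about 9–43% for 4/19 and 11–36% for 8/39.

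For paired seen-versus-phone availability in all 97, the half-width is 1.96 × √(d/97). That is 6.3 points at d = 10%, 8.9 at 20% and 10.9 at 30%. The mode effect detectable with 80% power is 9.0, 12.7 and 15.6 points.

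**The case against.** Several arguments on the other side have force.

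- **Direction.** A reader might infer that phone self-reports inflate stock, so that any improvement would be an artefact. The documents do not support this. Evaluation Effects says only that there is some risk, and its example is staff requesting extra stock, not misreporting counts.
- **Data already in hand.** A reader might infer that 97 in-person stock records are available. Missing Data says only that the facilities were visited and contact details collected. It does not say how many stock modules were completed, or that the 97 represent the 251.
- **Correcting the phone rounds.** It is tempting to adjust each remote estimate by the measured miss rate. That could create a false change, because the plan says stock-out data in general rest on records and recall, so visits can miss old stock-outs too. Suppose true stock-outs are 40% in both rounds and 80% are detected in both modes. Then 32% is observed each time and the change is correctly zero. Correcting the phone round alone gives 32/0.80 = 40% against 32%, a false 8-point worsening.
- **Partial handling.** The plan warns that refined tools may change how variables are measured, tracks comparator medicines, masks the focus of the study, and makes the current level its leading question.

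The first three stand and limit the remedy. The fourth does not remove the problem. The measurement warning is tied to the tools. The mean-availability covariate in Eq 3c and Eq 4c could absorb a shift common to all medicines only if measured in both phases and entered by round, and it appears to include peds-Amox itself. The 20% back-checks are re-interviews, with no physical count described.

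**Conclusion.** The concern holds as a confounding and disclosure point. In every remote-round comparison β1 is the true change plus any mode shift, and nothing planned can split them. This rests on Phase I Round 1 having been collected by visit, which is strongly implied and which the sponsor should state.

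The size is unknown. The 38% false-positive rate for a 5-point shift is an illustration under assumed power and sidedness, before the Holm adjustment, and not an estimate of bias.

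A reader might go further and conclude that the in-person eighth round should become the confirmatory test. The documents do not require that. It is a design preference, and the analysis of that round belongs to a companion document that may already plan the comparison.

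**What to change.** 1. **State and disclose.** Say how Phase I Round 1 was collected. List survey mode under Other Study Limitations as a limitation of β1, and correct the wording there that still describes verification on the day of the visit.
2. **Pre-specify a mode check as a sensitivity analysis**, limited to those of the 97 visited facilities with usable in-person stock data. Report (a) the share of facilities seen without peds-Amox that report a 90-day stock-out by phone, and (b) paired seen-versus-phone availability for peds-Amox and the comparator medicines. Give each a 95% CI. State the caveats: an 8–13 week gap with real stock movement (which affects (b) most), recall or record error, no in-person comparator for (a), and a non-random subset. Confirm the year of the visits.
3. **Report a tipping point for each remote-round change**, instead of a correction applied to the phone rounds only. For a positive estimate, a mode shift equal to the lower confidence limit removes significance, and a shift equal to the estimate removes the change. For example, an estimate of 8.51 with SE 3.04 has a lower limit of 8.51 − 1.96 × 3.04 = 2.55, so a shift of about 2.6 points would suffice, and less after the Holm adjustment.
4. **Cross-refer to the in-person eighth round** as the same-mode comparison with Phase I Round 1, without making it the confirmatory test in this plan.

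The cost is some text and a modest extra analysis, with no new data collection. The plan was drafted before any Phase II data were analyzed, so pre-specification is still credible. The downside is that the check rests on few facilities: it can reveal a large mode effect but cannot exclude one near 8.51 points.
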